| EDB | extensor digitorum brevis muscle |
| EOS | end of study |
| ESR | erythrocyte sedimentation rate |
| FEF | forced expiratory flow |
| FEV | forced expiratory volume |
| FF | fat fraction |
| FIG4 | Factor-induced Gene 4 |
| FVC | forced vital capacity |
| GCP | Good Clinical Practice |
| GGT | gamma-glutamyl transferase |
| IRB | Institutional Review Board |
| MFF | muscle fat fraction |
| MRI | magnetic resonance imaging |
| NCS | nerve conduction study |
| ONLS | Overall Neuropathy Limitation Scale |
| pCMT-QOL | pediatric CMT quality of life |
| PEDI | Pediatric Evaluation of Disability Inventory |
| PEDICAT | PEDI Computer Adaptive Test |
| PedsQL | Pediatric Quality of Life Inventory |
| PFT | pulmonary function test |
| PRO | patient-reported outcome |
| PT/INR | prothrombin time test and international normalized ratio |
| PTT | partial thromboplastin time test |
| SAE | serious adverse event |
| TA | tibialis anterior muscle |
| TUG | Timed Up & Go |

CLINICAL PROTOCOL SYNOPSIS

| | |
|-----------------------------|---|
| Study Title | A Prospective Natural History and Outcome Measure Discovery Study of Charcot-Marie-Tooth Disease, Type 4J |
| Sponsor | Elpida Therapeutics SPC |
| Trial Phase | Observational |
| Study Population | Subjects with a genetically confirmed diagnosis of CMT4J will be included. |
| Investigational Site | 
4 US sites
 
 • University of Texas Southwestern Medical Center /Children’s Health • University of Iowa • NIH (National Institute of Neurological Disorders and Stroke) • Stanford School of Medicine |
| Study Objectives | 
 • To gain a better understanding of the course of illness • To collect data about genotype-phenotype correlations to allow for better prediction of disease progression based on genetic information • To investigate and follow at long term different outcome measurements (e.g., motor, quality of life, radiologic and electrophysiological) • To expedite research and access to new therapies for rare conditions like CMT4J |
| Study Design | A multicenter, longitudinal, prospective observational natural history study of subjects with a molecular confirmed diagnosis of CMT4J |
| Eligibility Criteria | 
Inclusion Criteria:
 
 1. Male or female, all ages 2. A molecularly-confirmed diagnosis of CMT4J (confirmed by a CLIA certified, CE-marked, or equivalent lab): Genomic DNA mutation analysis demonstrating 1) bi-allelic pathogenic and/or likely pathogenic variants (by ACMG criteria) in the FIG4 gene, or 2) bi-allelic variants with one pathogenic and/or likely pathogenic variant in trans with a variant of uncertain significance if laboratory evidence and expert consensus exists in support of loss of FIG4 function exists. 3. Informed consent from patients 18 years or older who are able to provide consent and from caregivers; parent(s)/guardian(s) providing consent for subjects younger than 18 years at Screening and patients older than 18 years unable to provide informed consent 4. Informed assent of patients younger than 18 years at Screening who are able to provide assent 5. Able and willing to comply with the study protocol, including travel to Study Center, procedures, measurements and visits 
Exclusion Criteria:
 
 1. Any known genetic abnormality, including chromosomal aberrations that confound the clinical phenotype 2. Current participation in an interventional or therapeutic study 3. Receiving an investigational drug within 90 days of the Baseline Visit |

| | |
|-----------------------|---|
| | 
 4. Prior or current treatment with gene or stem cell therapy 5. Any other diseases which may significantly interfere with the assessment of CMT4J 6. Have any other conditions, which, in the opinion of the Investigator or Sponsor would make the subject unsuitable for inclusion or could interfere with the subject participating in or completing the study |
| Study Duration | 
Subject visits will occur every 12 months \pm 4 weeks for up to 2 years for the initial period with extension of up to 60 months if feasible. No investigational product will be used during the study.
 |
| Assessments | 
Clinical Assessments:
 
 • Electrophysiology • Nerve Conduction Studies (NCS) • Pulmonary Function Tests (PFTs) • Scoliosis series X-ray • Magnetic Resonance Imaging 
 1. Thigh and calf muscle without contrast 2. Brain without contrast 
Neuropsychological Assessments:
 
 • Vineland Adaptive Behavior Score, 3rd edition • Bayley Scales of Infant and Toddler Development-III • Wechsler Abbreviated Scale of Intelligence Second Edition / Wechsler Preschool & Primary Scale of Intelligence Fourth Edition (WASI-II / WPPSI-IV) • Stanford-Binet V (SB5) 
Physical Therapy Assessments:
 
 • PEDICAT • CMTPedS for subjects 5 to 17 years of age • CMTInfS (< 4 years old) • CMTNSv2 for subjects >18 years of age • CMT-FOM for subjects > 18 years of age • Timed Up and Go Test (TUG) 
Questionnaires:
 
 • PedsQL (2-18 years) • ONLS (18 years and older) • pCMT-QOL PRO (8-18 years) • pCMT-QOL parent proxy (8-18 years) • pCMT-QOL parent proxy (0-7 years) • CMT Health Index (CMTHI) for >18 years of age |

| | |
|-----------------------------------|---|
| | 
Exploratory Assessments:
 
• Blood collection for exploratory biomarker• Wearable devices• Optional skin biopsy |
| STATISTICAL CONSIDERATIONS | 
The sample size of 20 subjects is expected to provide sufficient insights into the natural history of individuals with CMT4J, a rare disease, to provide exploratory and descriptive results and guide the design of future studies of CMT4J. No formal sample size estimation was performed for this study. Parametric and non-parametric tests will be used to analyze possible associations between clinical, radiographic, and laboratory data. The tests will be selected based on the question being asked of the database. This database will be used to analyze multiple medical issues among subjects with confirmed CMT4J.
 |

1 INTRODUCTION: BACKGROUND INFORMATION AND SCIENTIFIC RATIONALE

1.1 Introduction and Purpose

Charcot-Marie-Tooth (CMT) disease is a group of inherited peripheral neuropathies, affecting 1 in 1,214 (1) to 2,500 (2). CMT can affect both females and males of all ethnicities.

CMT is classified according to the type of nerve damage (demyelinating vs. axonal) and its type of inheritance (autosomal recessive, dominant or X-linked). Mutations in more than 80 genes cause CMT. Most of the CMT neuropathies are demyelinating, especially CMT1A which comprises 60 to 65% of cases.

CMT4J is a rare autosomal recessive, peripheral motor demyelinating neuropathy caused by biallelic pathogenic variants in the FIG4 gene. CMT4J is characterized by childhood onset gait abnormalities and balance difficulties, that rapidly progress to muscle weakness and muscle atrophy during the teen or adult years. Onset can be acute or sub-acute, mimicking an acquired neuropathy and often misdiagnosed as chronic inflammatory demyelinating polyneuropathy (CIDP), or a subacute presentation of Guillain-Barre Syndrome. Involvement can be asymmetric and can affect distal as well as proximal musculature. Although sensory symptoms are minimal, examination may reveal decreased response to touch, pin prick, or vibration distally. Bulbar and cranial nerve functions are often spared; intellect is often normal.

This study is designed to investigate the clinical characteristics and natural history of CMT4J. We aim to follow subjects with a molecularly confirmed diagnosis of CMT4J longitudinally to collect standardized clinical data to evaluate epidemiological characteristics, clinical course, and to identify potential outcome measures which may be used in future clinical trials. Clinical data collection will include medical history and physical exam, hematology and biochemical analyses, calf muscle imaging, nerve conduction studies, pulmonary function testing and neuropsychological assessments.

The study will be conducted in accordance with the protocol, Good Clinical Practice (GCP), and the applicable regulatory requirements.

1.2 Background and Rationale

There is no causative treatment available for CMT, but therapeutic clinical trials for the most common types of CMT, like CMT1A, are ongoing. Most recently, animal models have demonstrated the possibility of treating some types of CMT, like CMT4J, with gene transfer therapy through viral vectors. To be able to understand the condition over time and evaluate these therapies at long term, natural history studies are indispensable. This study investigates the natural history of CMT4J.

1.3 Concise Summary of Project

This is a multicenter, longitudinal, prospective observational natural history study of subjects with a molecularly confirmed diagnosis of CMT4J. We plan to enroll 20 subjects of any age into a uniform protocol for follow-up and evaluations. We will obtain demographic and medical history information. Natural history data will be collected prospectively on an annual basis and may include physical/neurological exams, standard laboratory tests, CMT outcome and disability measures, neuropsychological tests, nerve conduction studies (NCS), and imaging studies (muscle MRI). Pulmonary function test (PFT) and scoliosis series x-ray Subject visits will occur every 12 months

± 4 weeks for up to 2 years. Subjects who terminate from the study prior to Visit 3 will undergo an early termination/end of study visit (EOS) if possible. The early termination/end of study visit is comprised of the Visit 3 assessments. If needed, the Investigator may conduct unscheduled visits with Sponsor's approval. No investigational product will be used during the study.

Since CMT4J is a rare disease, there is a high likelihood that both national and international families may be interested in study participation.

OBJECTIVES

1.4 Study Objectives

- To gain a better understanding of the CMT4J disease course and phenotypic spectrum.
- To explore CMT4J genotype-phenotype correlations to allow for better prediction of disease progression based on genetic information.
- To evaluate candidate clinical trial outcome measures related to motor function, quality of life, radiology, and electrophysiology. To expedite research and access to new therapies for rare conditions like CMT4J.

2 STUDY ELIGIBILITY, ENROLLMENT AND CONSENTING

2.1 Target and Study Population

Subjects with a prior diagnosis of CMT4J will be included. CMT4J diagnosis will be made by both clinical manifestations and a confirmed genetic confirmation. Examples of clinical manifestations consistent with CMT4J, include but are not limited to, childhood onset gait abnormalities, poor balance, and accelerated, most commonly asymmetric, limb weakness and muscle atrophy, involving distal and proximal musculature.

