2.2 Subject Inclusion Criteria

Inclusion Criteria:

1. Male or female, all ages
2. A molecularly-confirmed diagnosis of CMT4J (confirmed by a CLIA certified, CE-marked, or equivalent lab): Genomic DNA mutation analysis demonstrating 1) bi-allelic pathogenic and/or likely pathogenic variants (by ACMG criteria) in the FIG4 gene, or 2) bi-allelic variants with one pathogenic and/or likely pathogenic variant in trans with a variant of uncertain significance if laboratory evidence and expert consensus exists in support of loss of FIG4 function exists.
3. Informed consent from patients 18 years or older who are able to provide consent and from caregivers; parent(s)/guardian(s) providing consent for subjects younger than 18 years at Screening and patients older than 18 years unable to provide informed consent
4. Informed assent of patients younger than 18 years at Screening who are able to provide assent

5. Able and willing to comply with the study protocol, including travel to Study Center, procedures, measurements and visits

Exclusion Criteria:

1. Any known genetic abnormality, including chromosomal aberrations that confound the clinical phenotype
2. Current participation in an interventional or therapeutic study
3. Receiving an investigational drug within 90 days of the Baseline Visit
4. Prior or current treatment with gene or stem cell therapy
5. Any other diseases which may significantly interfere with the assessment of CMT4J
6. Have any other conditions, which, in the opinion of the Investigator or Sponsor would make the subject unsuitable for inclusion or could interfere with the subject participating in or completing the study

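### Does Protocol section 2.1 add a clinical entry requirement that inclusion criterion 2 does not contain?

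*Protocol*

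**What the plan says.** Section 2.1 opens with "Subjects with a prior diagnosis of CMT4J will be included" and continues: "CMT4J diagnosis will be made by both clinical manifestations and a confirmed genetic confirmation". It then gives examples of manifestations in an open list, with no minimum set or threshold.

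Criterion 2 in section 2.2, printed identically in the synopsis, requires "A molecularly-confirmed diagnosis of CMT4J (confirmed by a CLIA certified, CE-marked, or equivalent lab" and defines this by laboratory findings. One route is "Genomic DNA mutation analysis demonstrating 1) bi-allelic pathogenic and/or likely pathogenic variants (by ACMG criteria) in the FIG4 gene". The other accepts one such variant in trans with a variant of uncertain significance, "if laboratory evidence and expert consensus exists in support of loss of FIG4 function exists". Neither route names a symptom or sign, and no other inclusion or exclusion criterion requires one.

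The shorter population statements use the same language. The synopsis has "Subjects with a genetically confirmed diagnosis of CMT4J will be included", section 1.1 has "We aim to follow subjects with a molecularly confirmed diagnosis of CMT4J longitudinally", and section 1.3 describes a "natural history study of subjects with a molecularly confirmed diagnosis of CMT4J".

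**The concern.** Section 2.1 joins the two elements with the word both, and it stands in the eligibility chapter beside the numbered criteria. A reader may take it as an entry condition that section 2.2 left out. The person who would fall between the two texts is easy to picture. The disease is recessive with childhood onset (section 1.1), all ages may enrol, an infant scale is provided, and families may refer themselves (section 2.3). A young sibling with two qualifying variants and no signs yet would meet criterion 2 but not the description in section 2.1.

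Two things would be at stake. The objectives in section 1.4 include the phenotypic spectrum and genotype-phenotype correlation. Requiring manifestations selects subjects on phenotype, and not requiring them does not. If the four sites read the text differently, that selection would differ between them. In addition, section 8 lists the enrolment of ineligible subjects as a major deviation, so the same enrolment could be counted as correct at one site and as a deviation at another.

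**Working it through.** There is no figure in the plan to reproduce. Section 10 states that the sample size was not formally estimated, and the question is one of wording. The check is to set the relevant texts side by side and see which of them operates when a person is screened.

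| Place in the protocol | What it does | Clinical sign required? |
|---|---|---|
| 2.1 | Describes the target population | Yes, as part of the diagnosis |
| 2.2 and synopsis, criterion 2 | Numbered entry rule | No |
| Synopsis (population), 1.1, 1.3 | Short population descriptions | Not named |
| 2.4 | How eligibility is confirmed | Not named; genetic documents are reviewed |
| Appendix 1 | When the criteria are checked | Criteria at Screening only |

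**Step 1: is it a flat contradiction?** Not quite. Section 2.1 speaks of people who already carry a diagnosis. Criterion 2 can be read as setting the laboratory standard for the genetic half of that diagnosis. Against this, the definition that follows the colon in criterion 2 is purely molecular, apart from the functional evidence and expert consensus on the uncertain-variant route. The short descriptions do not decide the matter, because each still uses the word diagnosis. The synopsis criterion is the section 2.2 text printed again, so it adds no independent support.

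**Step 2: which text operates?** Under section 2.4 the investigator reviews the genetic documentation to confirm eligibility, and must do so before travel or a site visit is arranged. Manifestations are not mentioned. In Appendix 1 the inclusion and exclusion check is marked at Screening only, while medical history, the diagnosis and disease history, and the neurological examination are first marked at Baseline. The CMT scales are marked at Screening, but nothing makes them a test for entry. Screening therefore runs on the numbered list and the genetic report, and section 2.1 has no procedure attached to it.

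**Step 3: what happens if a person without manifestations is enrolled?** The medical history item in section 3 (printed as 4.1) records time of symptom onset and progression, age at diagnosis and genetic results, and a detailed neurological examination is done at each visit. Symptomatic status at entry can be derived from these without a new data item. Such subjects can then be described separately or set aside in a given analysis.

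**Step 4: size.** The protocol gives no count or expected share of people with qualifying variants and no manifestations. If none present, the effect is 0. With at most 20 subjects, each one is at least 1/20 = 5% of the cohort. This is a unit of scale and does not show that any such person exists.

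**The case for a change.** The strongest case for a change is that the protocol never says the numbered criteria prevail. That is convention, and section 2.1 belongs to the same chapter. Section 2.4 shows what investigators look at, but it neither cites section 2.1 nor calls it descriptive. Exclusion criterion 6 does not help either, because it concerns conditions that make a subject unsuitable and does not say whether lack of signs disqualifies. Eligibility belongs in the protocol, so it cannot be left to a statistical analysis plan. One sentence would settle the matter.

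Much of this stands. No text expressly decides the case of a person with qualifying variants and no manifestations, and a site that treated section 2.1 as an extra condition could turn that person away. What does not stand is the step from there to a defect in the plan. A sentence confirming that section 2.2 governs would only record what section 2.4 and Appendix 1 already lead sites to do. The other repair, a numbered criterion requiring manifestations, would narrow the population. That is a design choice for the sponsor, and the inconsistency alone does not call for it.

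**Conclusion.** Section 2.1 is loosely worded against criterion 2, and the looseness is minor. No change to the plan follows. Screening works from the numbered criteria and the genetic documents. The data needed to recognise a subject without manifestations are collected anyway, and section 10 declares all analyses exploratory.

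The size is unknown from the protocol: zero if no such person presents, otherwise at least 5% of the cohort for each one. The conclusion rests on two assumptions: that the four sites screen as section 2.4 and Appendix 1 set out, and that onset history and the Baseline examination are recorded as planned. If the first failed at a site, the loss would be a few people not enrolled there, which would narrow the observed spectrum without invalidating the description of those who were enrolled.

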2.2 Subject Inclusion Criteria

Inclusion Criteria:

1. Male or female, all ages
2. A molecularly-confirmed diagnosis of CMT4J (confirmed by a CLIA certified, CE-marked, or equivalent lab): Genomic DNA mutation analysis demonstrating 1) bi-allelic pathogenic and/or likely pathogenic variants (by ACMG criteria) in the FIG4 gene, or 2) bi-allelic variants with one pathogenic and/or likely pathogenic variant in trans with a variant of uncertain significance if laboratory evidence and expert consensus exists in support of loss of FIG4 function exists.
3. Informed consent from patients 18 years or older who are able to provide consent and from caregivers; parent(s)/guardian(s) providing consent for subjects younger than 18 years at Screening and patients older than 18 years unable to provide informed consent
4. Informed assent of patients younger than 18 years at Screening who are able to provide assent

5. Able and willing to comply with the study protocol, including travel to Study Center, procedures, measurements and visits

Exclusion Criteria:

1. Any known genetic abnormality, including chromosomal aberrations that confound the clinical phenotype
2. Current participation in an interventional or therapeutic study
3. Receiving an investigational drug within 90 days of the Baseline Visit
4. Prior or current treatment with gene or stem cell therapy
5. Any other diseases which may significantly interfere with the assessment of CMT4J
6. Have any other conditions, which, in the opinion of the Investigator or Sponsor would make the subject unsuitable for inclusion or could interfere with the subject participating in or completing the study

2.3 Recruitment Methods

We plan to enroll up to 20 subjects into the study. The gender, race, and ethnic distribution of the accrued study population may not be representative of the general population but is expected to reflect those affected with the disease under study. Patients who currently seek medical care at a study site may be approached to participate in the study. For those patients who are followed at a study site, their treating physician will inform the patient and/or family of the study. Should the patient/family be amenable to learning more about the study, then a member of the research staff will speak with them about study participation. The patient/family will be given ample time to review the consent form and ask questions. The patient may enroll into the study at any time during their care.

Participants will be recruited through clinician or self-referral. The study will be posted at clinicaltrials.gov to aid recruitment. An IRB-approved study advertisement will also be made available to patient and professional organizations such as Cure CMT4J and the Inherited Neuropathies Consortium, respectively. The approved advertisement may be posted on patient organization websites/social media accounts and may also be made available at scientific/medical/patient conferences.

Participant selection will be equitable considering the rarity of CMT4J. All ages within the specified range, races, and both sexes will be accepted. There will be no restriction based on geographic location. The study team will enhance retention by sending email reminders to participants prior to scheduled visits and will be available to answer any study-related questions between visits.

If a patient/family contacts the study personnel, they will send a consent form to the patient/family and answer their questions accordingly. If the patient/family is interested in establishing care at a study site, the study staff will connect them with the proper department.

2.4 Consenting Process and Review of Genetic Diagnosis

Documentation of genetic confirmation will be reviewed by the Investigator prior to any on-site visits being arranged, in order to confirm eligibility. Each site will follow their IRB guidelines on consent processes for obtaining genetic test results prior to on-site patient visits.

The Sponsor is using a vendor to manage travel planning and expenses for the site and subjects. The vendor will act as a third-party working with both the site and subject to book travel (including flights, hotels, ground transportation, etc.) The vendor will bill the Sponsor directly for subject travel costs,

and any travel expenses incurred by the subject (e.g., meals, tolls, parking fees, etc.) will be reimbursed to the subject. Only the travel expenses of the subject and up to two caregivers will be covered. The Investigator must confirm eligibility of the subject prior to any travel or on-site visits being arranged. The subject will be asked to sign a vendor-specific data use consent prior to any travel arrangements. Once a potential subject expresses interest in study participation and chooses to travel to the site, the study staff will connect the subject to the vendor coordinator to sign the vendor data use consent and proceed with travel arrangements. This may be done prior to the subject signing the study's informed consent document.

Informed consent will be obtained from all subjects with sufficient capacity or from legal guardians/representatives of subjects with insufficient capacity to consent. Written or verbal assent will be obtained in accordance with Institutional Review Board (IRB) guidelines. Dissent from all subjects will be respected.

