APPENDIX 1: SCHEDULE OF EVENTS

| Study Day | Screening | Baseline | Month 12 | Month 24 |
|---|------------------|------------------|------------------|------------------|
| Windows | | (± 4 wks) | (± 4 wks) | (± 4 wks) |
| Informed Consent | X | | | |
| Medical Information | | X | X | X |
| Demographics | | | | |
| Medical History | | X | X | X |
| Family History | | X | | |
| CMT4J Diagnosis and History | | X | | |
| Clinical Procedures | | | | |
| Inclusion/Exclusion Criteria | X | | | |
| Vital Signs ^a | | X | X | X |
| Height and Weight | | X | X | X |
| Physical Exam ^b | | X | X | X |
| Neurological Exam ^c | | X | X | X |
| Urine Pregnancy (for female subjects) ^d | | X | X | X |
| Blood Collection for Future Exploratory Analysis ^e | | X | X | X |
| Skin biopsy (optional, any visit, only once) | | X | X | X |
| Adverse Events | | X | X | X |
| Concomitant Medications | | X | X | X |
| CMT Scales* | | | | |
| CMTpedS ^f | X | X | X | X |
| CMTInfS ^g | X | X | X | X |
| CMTNSv2 ^h | X | X | X | X |
| CMT-FOM ^h | X | X | X | X |
| CMT Health Index (CMTHI) ^h | X | X | X | X |
| Clinical Studies | | | | |
| Thigh and Calf MRI without contrast | | X | X | X |
| Brain MRI without contrast | | X | X | X |
| Nerve Conduction Study (NCS) ⁱ | | X | X | X |
| Pulmonary Function Test (PFT) ^j | | X | X | X |
| Scoliosis Series X-ray ^k | | X | X | X |
| Neuropsychological and Physical Therapy Assessments | | | | |
| Vineland Adaptive Behavior Scale | | X | X | X |
| PEDICAT ^l | | X | X | X |
| Bailey III | | X | X | X |
| WASI-II or WPPSI-IV | | X | X | X |
| Stanford Binet – V | | X | X | X |
| Timed up and go (TUG) | | X | X | X |
| Wearable devices | X | X | X | X |
| Questionnaires | | | | |
| PedsQL ^m | | X | X | X |
| Overall Neuropathy Limitation Scale (ONLS) (18 years and older) | | X | X | X |
| pCMT-QOL PRO (8 to 18 years) | | X | X | X |
| pCMT-QOL (8 to 18 years parent-proxy) | | X | X | X |
| pCMT-QOL (0 to 7 years parent-proxy) | | X | X | X |

-
- ^a Temperature, pulse, blood pressure measured in one arm or leg after the patient has been seated for ~ 5 minutes.
 - ^b Exam of heart, lungs, abdomen, back, and extremities; height and weight; head circumference
 - ^c Includes evaluation of cranial nerves, muscle tone, muscle strength, sensation, gait, coordination and deep tendon reflex testing, handheld dynamometry

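### Do the Screening marks for the CMT scales and wearables in Appendix 1 break the annual visit plan or the pre-travel eligibility rule?

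*Protocol*

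**What the plan says.** Appendix 1 has four columns: Screening, Baseline, Month 12 and Month 24. Six assessment rows are marked in all four, for example "CMTpedS ^f | X | X | X | X" and "Wearable devices | X | X | X | X". The other four are CMTInfS, CMTNSv2, CMT-FOM and CMTHI. The only other Screening marks are informed consent and eligibility ("Inclusion/Exclusion Criteria | X"). Other assessments begin at Baseline, as in "Timed up and go (TUG) | | X | X | X". The window cell for Screening is empty, while Baseline, Month 12 and Month 24 each carry ± 4 weeks.

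Section 1.3 gives the visit plan: "Natural history data will be collected prospectively on an annual basis", with visits 12 months apart for up to 2 years. For subjects who leave early it says "The early termination/end of study visit is comprised of the Visit 3 assessments".

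Section 2.4 states that "The Investigator must confirm eligibility of the subject prior to any travel or on-site visits being arranged". It also says, of the travel vendor's data consent and the travel arrangements, "This may be done prior to the subject signing the study's informed consent document".

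Section 3 defers to Appendix 1 for how often each assessment is done. Section 9.3.1 counts adverse events from signature of the consent form, whereas the Adverse Events row of Appendix 1 starts at Baseline.

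**The concern.** Two things look wrong.

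First, the annual plan implies three assessment points, yet six rows have four. If sites follow the table literally, a subject takes the same scale twice before follow-up, at an interval that is not clearly fixed. If some of the four sites do this and others do not, exposure to the scales before the Baseline value differs by site, in a study of about 20 subjects that aims to evaluate these scales as candidate outcome measures.

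Second, the only eligibility mark is at Screening, and Section 2.4 wants eligibility settled before travel. If Screening is therefore remote, four of the five scales (CMTPedS, CMTInfS, CMTNSv2 and CMT-FOM, all listed in the synopsis as physical therapy assessments) could hardly be done there, and scheduled items would be logged as missed. If Screening is on site, the only scheduled eligibility check seems to come after travel has been arranged.

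At stake would be the comparability of the first measurement across sites and the completeness record of the main scales.

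**Working it through.** The protocol makes no formal sample size calculation, so there is no design figure to reproduce. The check is a count of marks followed by a comparison of sections.

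**Count.**
- Marks per affected row: 4. Marks for the Timed Up and Go, nerve conduction, lung function and MRI: 3. Surplus: 4 − 3 = 1 per applicable measure per subject.
- By the age footnotes, a child under 4 or aged 5 to 17 has 1 applicable CMT scale, and an adult has 3 (CMTNSv2, CMT-FOM, CMTHI). The surplus is therefore 1 or 3 scale administrations per subject, plus wearables. A study total would need the age mix, which the protocol does not give. It would still be only a count of table marks, not an effect on any result.
- Each affected row has four marks for four columns. A column shift when the PDF was read would move a mark, not add one, so the marks are taken as real.

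**Against the annual plan.** With Baseline as Visit 1, Month 12 is Visit 2 and Month 24 is Visit 3, which agrees with Section 1.3. A measurement taken before Baseline leaves the 12-month spacing intact. Counting Screening as Visit 1 would make Visit 3 Month 12, which does not fit Visit 3 as the last visit. Even then the early-termination assessments would be the same, because the Month 12 and Month 24 columns carry identical marks.

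**Against Section 2.4.** That section opens by saying that the investigator reviews the genetic documentation before an on-site visit is arranged, for the purpose of confirming eligibility. Inclusion criteria 3 and 4 in Section 2.2 are consent and assent, with minority age judged at Screening. Since Section 2.4 allows travel arrangements before study consent, those two criteria need not be met before travel is arranged. The pre-travel step is thus most naturally the genetic review, and the Screening mark is the formal record of all criteria. An on-site Screening is consistent with this.

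**What each reading does to the data.**
1. Screening and Baseline on separate days, scales done twice: two values before follow-up, with Baseline as the natural reference and the pair usable for test-retest.
2. Screening and Baseline on one trip, scales done once: one value, which serves as Baseline.
3. Screening remote, in-person scales not done: the Screening cell is empty and Baseline is unaffected.

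In all three, change to Month 12 and Month 24 is measured from the same Baseline column. Section 5 ties case report forms to each scheduled visit and each protocol assessment, so an analyst can see who had a Screening value.

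**Adverse events.** Section 9.3.1 makes events reportable from consent. An entry made at the Baseline visit can cover the time since consent, so the later start of the table row loses nothing.

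**The case for a change.** The strongest case for acting is that Section 3 makes Appendix 1 govern frequency, so the marks are instructions and not decoration. Nothing in the text says that a repeat before follow-up is intended. Section 2.2 treats Screening and the Baseline Visit as distinct points, and the ± 4 weeks at Baseline has no stated anchor, so the gap between them is not clearly bounded. If prior exposure improves performance, Baseline would be a second attempt at some sites and a first at others, and the apparent change to Month 12 would be mixed with that. Section 8 also names unperformed assessments and confounding of key outcome measures among major deviations. The edit would be small.

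Most of the factual part stands: the marks are unexplained, and the place and timing of Screening are not given. The consequence does not stand. The documents give no practice effect, and any difference in exposure would be visible in the recorded visits. Section 10 calls every analysis exploratory. Section 8 also gives a missed laboratory test or missed visit as an example of a minor deviation. Nor is deleting the marks clearly better: a repeat measurement before follow-up could serve the Section 1.4 objective of evaluating outcome measures, at the price of some burden.

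**Conclusion.** The concern does not call for a change to the plan. Appendix 1 has an unexplained Screening mark in six rows and an Adverse Events row that starts one column late. These are clerical points or gaps in detail that sites and analysts can fill sensibly. The conflict with Section 2.4 largely disappears once its pre-travel check is read as the genetic-document review that the same section describes. The conflict with the annual plan is only apparent, since a measurement before Baseline does not alter 12-month visits.

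The size is one additional administration per applicable measure per subject (four against three), with no effect on a sample size, a reference value or a planned conclusion. Whether to drop the marks or keep them as a repeat baseline is a fair trade-off between burden and test-retest information.

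This rests on three assumptions: Baseline is used as the reference, as the schedule's layout implies; Screening values are recorded under their own visit; and the analyses remain exploratory, as Section 10 states.
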